### Maximum dosing

A maximum loading dose of cefuroxime 2332 mg

A maximum hourly dose of continuous infusion of 1226 mg/hour.

These doses will be administered for a maximum of 6 hours.

Route of administration: Intravenous

### 8.7 Dosage modifications

Dose modifications: Dosages will be modified according to renal function as described in section 8.6.

Stopping rules: Acute adverse event, duration of surgery 6 hours.

Procedures in the event of toxicity reactions: Antibiotic treatment will be stopped.

### 8.8 Known drug reactions and interaction with other therapies

The cefuroxime SPC reports: "Cephalosporin antibiotics at high dosage should be given with caution to patients receiving potent diuretics or aminoglycosides, as these combinations are suspected of adversely affecting renal function. Clinical experience has shown that this is not likely to be a problem at the recommended dose levels."

Given the short duration of treatment, and so low total drug amounts administered compared to daily treatment regimes, we will allow patients on diuretics (principally furosemide) and aminoglycosides to enter the study.

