### 6.2 Exclusion criteria

- Unable to consent
- Pregnancy
- Expected duration of surgery <2hours
- Creatinine clearance <40ml/min
- Individual level microbiological advice for non cefuroxime based prophylaxis
- Cephalosporin allergy
- Penicillin allergy (hypersensitivity reaction only)
- Coumarin (warfarin and acenocoumarol) treatment
- Active blood borne virus infection e.g. HIV, hepatitis.
- Seizure history
- Concurrent use of probenecid
- Current participation in a research project aimed at reducing SSIs
- Antibiotics for treatment of a systemic Gram negative infection within 2 hours of initiation of surgery (Vancomycin, Teicoplanin, Daptomycin, Linezolid, Flucloxacillin. Nitrofurantoin and Clarithromycin would be permissible antibiotics without systemic Gram negative antibiotics).
- A current diagnosis of an SSI at the time of study entry.
- STARR procedures
- Weight <30kg or >110kg

Duration of the risk mitigation measures: 24 hours

MPs are not teratogenic

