## 8.2 Legal status of the drug

Cefuroxime

- Licensed at 1.5g 8 hourly dosing and 3g 8 hourly (meningitis)
- Indication: No BNF indication for surgical prophylaxis, although BNF provides dosing information for Surgical prophylaxis, 1.5 g by intravenous injection up to 30 minutes before the procedure.

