**16. APPENDICIES**

**16.1 Appendix 1-Risk**

Risks associated with trial interventions

- LOW ≡ Comparable to the risk of standard medical care
- MODERATE ≡ Somewhat higher than the risk of standard medical care
- HIGH ≡ Markedly higher than the risk of standard medical care

Justification: Briefly justify the risk category selected and your conclusions below (where the table is completed in detail the detail need not be repeated, however a summary should be given):

The intervention antibiotic prophylaxis is an evidence based intervention.

The method of administering the intervention, continuous infusion, is an established method of intervention, and used routinely in many health care systems.

The maximum loading dose of cefuroxime recommended in this study, 2332 mg, is below the SPC single dose recommended for dosing cefuroxime of 3000mg.

The maximum total dose of cefuroxime recommended in this study, 9688mg over 6 hours, is comparable to that in the drug SPC for treating meningitis, 3000mg 8 hourly (6000mg infused in an 8 hour period).

Beta-lactam therapy is established as a safe treatment. High dose beta-lactam therapy is routinely administered e.g. 2400mg benzylpenicillin 4 hourly for treatment of endocarditis, amoxicillin 2000mg four hourly for endocarditis, flucloxacillin 2000mg 4 hourly for endocarditis, piperacillin 4000mg 8 hourly for severe infections.

What are the key risks related to therapeutic interventions you plan to monitor in this trial?		How will these risks be minimised?		
MP/Intervention	Body system/Hazard	Activity	Frequency	Comments
Cefuroxime	Gastrointestinal tract/Clostridium difficile associated diarrhoea	Routine clinical assessment	Continuous while a hospital in-patient	
Cefuroxime	Hepatobiliary disorders	Liver function test (blood)	Clinically driven testing	
Cefuroxime	Blood and lymphatic system disorders	Full blood count	Clinically driven testing	
Cefuroxime	Skin and subcutaneous tissue disorders	Routine clinical assessment	Continuous in-patient assessment	
Cefuroxime	Renal and urinary disorders	Renal function monitoring (blood tests)	Clinically driven testing	
Cefuroxime	General disorders and administration site conditions	Injection site reactions which may include pain and thrombophlebitis	Routine clinical assessment	

Outline any other processes that have been put in place to mitigate risks to participant safety (e.g. DMC, independent data review, etc.)

MHRA assessment of the trial protocol

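### Section 8.8 admits patients on potent diuretics or aminoglycosides because total drug amounts are low against daily regimes, a premise that fails for part of Table 7 and conflicts with the stated maximum dose

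*Combined protocol and SAP*

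**What the plan says.** Section 8.8 reproduces a caution from the product label: cephalosporins at high dosage, combined with potent diuretics or aminoglycosides, are suspected of harming renal function. The label's reassurance is limited to recommended dose levels. The protocol then gives its reason for admitting these patients: "Given the short duration of treatment, and so low total drug amounts administered compared to daily treatment regimes, we will allow patients on diuretics", and the sentence goes on to include aminoglycosides.

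Four other places bear on that reason.

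- **Section 8.2** gives the licensed doses ("Licensed at 1.5g 8 hourly dosing and 3g 8 hourly (meningitis").
- **Section 8.6, Table 7** sets the loading dose and hourly infusion by weight band (30 to 110 kg) and creatinine clearance. Section 6.2 excludes weights outside 30 to 110 kg.
- **Maximum dosing**, after Table 7, states "A maximum loading dose of cefuroxime 2332 mg", then "A maximum hourly dose of continuous infusion of 1226 mg/hour", then "These doses will be administered for a maximum of 6 hours". The Trial Summary repeats these caps.
- **Appendix 1 (Risk)** adds them up: "The maximum total dose of cefuroxime recommended in this study, 9688mg over 6 hours". It calls this comparable to the meningitis regimen, which it counts as 6000 mg in 8 hours.

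On eligibility, Section 6.2 excludes "Antibiotics for treatment of a systemic Gram negative infection within 2 hours of initiation of surgery" and names some permissible antibiotics. No aminoglycoside is among them.

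On monitoring, Appendix 1 lists renal and urinary disorders among the key risks to monitor ("Renal function monitoring (blood tests"), at a frequency that is clinically driven.

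**The concern.** The amount of drug is the stated reason for admitting patients whom the quoted caution singles out. Short duration is not offered as a separate reason: the sentence uses it to arrive at a low total. If the total is not low for some eligible patients, the reason fails for them, and the label's reassurance, limited to recommended dose levels, cannot simply be carried over.

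Two things follow. The safety rationale for entry would rest on a statement that the protocol's own figures do not bear out. And a renal difference between arms in this group would be hard to see: neither the post-operative data list in Section 7.6 nor the schedule in Appendix 4 names a renal measure, and blood tests are left to clinical need.

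**Working it through.** **1. Reproduce the stated maximum.** The inputs are the caps in Maximum dosing.

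2332 + 6 × 1226 = 9688 mg, exactly the Appendix 1 figure.

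**2. Licensed daily totals, from Section 8.2.**

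- Standard: 3 × 1500 = 4500 mg.
- Meningitis: 3 × 3000 = 9000 mg.

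The cap is 9688 / 4500 = 2.15 times the standard day and 9688 / 9000 = 1.08 times the meningitis day.

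**3. What Table 7 gives.** The 6-hour total is the loading dose plus 6 times the hourly rate, in mg. Totals above 4500 are in bold.

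| Weight (kg) | CrCl 40-50 | 50-60 | 60-70 | 70-80 | 80-90 | >90 |
|---|---|---|---|---|---|---|
| 30-40 | 1385 | 1559 | 1727 | 1901 | 2069 | 2327 |
| 40-50 | 1783 | 2005 | 2221 | 2443 | 2665 | 2995 |
| 50-60 | 2182 | 2446 | 2716 | 2986 | 3256 | 3658 |
| 60-70 | 2574 | 2892 | 3210 | 3528 | 3846 | 4320 |
| 70-80 | 2972 | 3338 | 3704 | 4070 | 4436 | **4988** |
| 80-90 | 3371 | 3785 | 4199 | **4613** | **5033** | **5651** |
| 90-100 | 3763 | 4231 | **4693** | **5155** | **5623** | **6319** |
| 100-110 | 4161 | **4671** | **5187** | **5697** | **6213** | **6981** |

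- Above 4500 mg: 1 + 3 + 4 + 5 = 13 of 48 cells, all at 70 kg or more.
- Above 9000 mg: none.
- Highest: 1851 + 6 × 855 = 6981 mg, which is 6981 / 4500 = 1.55 standard days and 6981 / 9000 = 0.78 meningitis days.

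**4. Shorter operations.** Section 2.1 expects 53% of operations to last under 3 hours and 95% under 6. At 3 hours the highest cell gives 1851 + 3 × 855 = 4416 mg, so no cell exceeds 4500 mg. The highest cell passes 4500 mg at (4500 − 1851) / 855 = 3.1 hours. The last of the 13 to do so (80-90 kg, CrCl 70-80) passes it at (4500 − 1499) / 519 = 5.8 hours.

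**5. The caps against Table 7.** In the top row, the mid-band weight of 105 kg implies 1851 / 105 = 17.63 mg/kg loading and 855 / 105 = 8.14 mg/kg/h infusion; the other rows give nearly the same values. On that assumption:

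- a patient at exactly 110 kg would reach 110 × (1851 + 6 × 855) / 105 = about 7313 mg;
- the caps correspond to about 132 kg (loading) and 151 kg (infusion), both above the 110 kg entry limit.

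**6. Control arm.** At 1.5 g four-hourly, an operation approaching 6 hours carries 2 × 1500 = 3000 mg. In 19 of 48 cells (6 + 6 + 4 + 2 + 1, from the lightest band upwards) the 6-hour intervention total is below 3000 mg.

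**The case against.** The strongest reply is that 9688 mg is a ceiling that no eligible patient reaches under Table 7. That stands. A reader might infer from Appendix 1 that trial patients receive more than a full meningitis day in 6 hours; Table 7 does not support this. What the ceiling does show is that Table 7, Maximum dosing and Appendix 1 do not agree.

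Second, exceeding even the standard day takes a heavier patient and a long operation. That also stands: 35 of 48 cells never exceed 4500 mg within 6 hours. The 13 cells are not 27% of patients, because the documents give no distribution of weight or creatinine clearance.

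Third, the phrase about daily regimes might mean multi-day courses, against which any 6-hour total is small. The wording allows this. But the quoted caution concerns high dosage and its reassurance concerns recommended dose levels, so a comparison of cumulative course totals would not answer it.

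Fourth, a reader might infer that a patient on an aminoglycoside is both admitted by 8.8 and excluded by 6.2. The documents do not establish that. Section 6.2 excludes treatment of a systemic Gram-negative infection within 2 hours of surgery, and it can be read as a specific limit on the general allowance in 8.8. Neither section says so, and that is the only gap.

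Fifth, a reader might infer that the extra exposure always falls on the intervention arm. At 6 hours it does not: in 19 cells the intervention total is below control.

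Finally, safeguards exist. Creatinine clearance under 40 ml/min is excluded, the infusion varies with clearance, adverse events run to day 30 and the data monitoring committee receives combined reports. They reduce the consequence but do not repair the stated reason.

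**Conclusion.** The concern holds in limited form. As a blanket reason for admitting patients on potent diuretics or aminoglycosides, the low-total premise is contradicted by Table 7 for 13 of 48 cells at 6 hours, by up to 1.55 standard licensed days. It is not contradicted at 3 hours, nor against the meningitis day on Table 7 doses. Separately, the 9688 mg maximum cannot be obtained from Table 7 within the entry weights, so Section 8.6, Maximum dosing and Appendix 1 need reconciling with each other.

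This rests on two assumptions: that the daily regimes meant are the licensed 24-hour totals in Section 8.2, and that the infusion runs the full 6 hours for the upper figures. The documents do not say how many of the 90 patients would be taking these drugs. The primary endpoint and its analysis are unaffected; the point concerns the safety rationale and the ability to see a renal difference.

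**What to change.** 1. Remove the low-total premise from Section 8.8.
2. Reconcile Sections 8.2, 8.6 (Table 7), Maximum dosing, 8.8, Appendix 1 and the caps repeated in the Trial Summary, and state the 6-hour totals that actually apply to eligible patients beside the 4500 and 9000 mg licensed days.
3. Have the sponsor re-justify, on those totals, the entry of patients on potent diuretics or aminoglycosides.
4. State in 8.8 that its aminoglycoside allowance is to be read with the 2-hour exclusion in 6.2, or otherwise reconcile the two.
5. Tabulate routinely obtained post-operative creatinine by arm, with recorded potent-diuretic and aminoglycoside use, for the oversight committee.

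The cost is a text correction and one descriptive table. Pre-operative concomitant medication and antibiotic history are already collected; the case report form would need fields for the creatinine results and peri-operative use. The table will be incomplete because testing is clinically driven, so it should show the number tested in each arm and be read as description only. If the sponsor then narrows entry, some patients may be lost. Which dose, cap or co-medication rule should apply is for the sponsor to decide.

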### 8.9 Concomitant medication

Predictable concomitant agents include the anaesthetic medication administered intra-operatively.

Anaesthetic medications: An exhaustive list of anaesthetic agents is not provided. Common anaesthetic agents are provided below:

Anaesthetic agent: Propofol

Analgesic/anaesthetics: Alfentanil, fentanyl, remifentanil

Anaesthetic agents: Suxamethonium, atracurium, vecuronium, rocuronium

Colo-Pro Pilot

Analgesia: Morphine, tramadol, paracetamol, NSAID, oxycodone

Anti-emetics: Ondansetron, dexamethasone, cyclizine, metoclopramide

Vasoconstrictors: Metaraminol, ephedrine, noradrenaline

Cephalosporins are not recognised as interacting with any anaesthetic agents.

### **8.10 Trial restrictions**

No contraindications whilst on the active phase of the trial.

Contraception needs not be used.

### **8.11 Assessment of compliance**

Patient compliance is not applicable to this trial.

Drug administration will be documented on research forms.

## 9 PHARMACOVIGILANCE

### 9.1 Definitions

Term	Definition
Adverse Event (AE)	Any untoward medical occurrence in a participant to whom a medicinal product has been administered, including occurrences which are not necessarily caused by or related to that product.
Adverse Reaction (AR)	
An untoward and unintended response in a participant to an medicinal product which is related to any dose administered to that participant.
 
The phrase "response to an medicinal product" means that a causal relationship between a trial medication and an AE is at least a reasonable possibility, i.e. the relationship cannot be ruled out.
 
All cases judged by either the reporting medically qualified professional or the Sponsor as having a reasonable suspected causal relationship to the trial medication qualify as adverse reactions.

Serious Adverse Event (SAE)	
A serious adverse event is any untoward medical occurrence that:
 
 
• results in death
 
• is life-threatening
 
• requires inpatient hospitalisation or prolongation of existing hospitalisation
 
• results in persistent or significant disability/incapacity
 
• consists of a congenital anomaly or birth defect
 
 
Other 'important medical events' may also be considered serious if they jeopardise the participant or require an intervention to prevent one of the above consequences.
 
NOTE: The term "life-threatening" in the definition of "serious" refers to an event in which the participant was at risk of death at the time of the event; it does not refer to an event which hypothetically might have caused death if it were more severe.

Serious Adverse Reaction (SAR)	An adverse event that is both serious and, in the opinion of the reporting Investigator, believed with reasonable probability to be due to one of the trial treatments, based on the information provided.
Suspected Unexpected Serious Adverse Reaction (SUSAR)	
A serious adverse reaction, the nature and severity of which is not consistent with the information about the medicinal product in question set out:
 
 
• in the case of a product with a marketing authorisation, in the summary of product characteristics (SmPC) for that product
 
• in the case of any other medicinal product, in the investigator's brochure (IB) relating to the trial in question
 

NB: to avoid confusion or misunderstanding of the difference between the terms "serious" and "severe", the following note of clarification is provided: "Severe" is often used to describe intensity of a

specific event, which may be of relatively minor medical significance. “Seriousness” is the regulatory definition supplied above.

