## 9.2 Operational definitions for (S)AEs

(S)AEs will be defined according to standard definitions, section 9.1.

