## 9.3 Recording and reporting of SAEs AND SUSARs

The period of time over which AEs, ARs, SAEs, SARs and SUSARs are to be monitored start at and finish at:

- For AEs / SAEs – 1st MP dose to day 30 post operation
- For ARs / SARs and SUSARs – 1st MP dose to day 30 post operation

SAEs occurring in a research participant should be reported to the main REC/Sponsor where in the opinion of the Chief Investigator (CI) the event was:

- Related – that is, it resulted from administration of any of the research procedures, and
- Unexpected – that is, the type of event is not listed in the protocol as an expected occurrence.

Adverse events which are expected occurrences and relevant to the study population includes but is not limited to (multiple post-operative complications occur routinely in this cohort undergoing extensive colorectal surgery):

- Those listed in the Summary of Product Characteristics
- Surgical site infections
- All other infections including respiratory, urinary and skin infections (including fungal infections).
- Vascular events e.g. emboli, thrombosis, haemorrhage
- Failure of the surgical procedure e.g. anastomotic breakdown, fistulation
- Procedures i.e. urinary catheterisation, venous access device.

**SUSARs** occurring from the time of **randomisation** until 30 days post cessation of trial treatment must be recorded on the AE form and faxed to the Sponsor within one working day of the research staff becoming aware of the event. Once all resulting queries have been resolved, the Sponsor will request the original form should also be posted to the Sponsor and a copy to be retained on site.

For each **SUSARs** the following information will be collected:

- full details in medical terms and case description
- event duration (start and end dates, if applicable)
- action taken
- outcome

- seriousness criteria
- causality (i.e. relatedness to trial drug / investigation), in the opinion of the investigator
- whether the event would be considered expected or unexpected.

Any change of condition or other follow-up information should be faxed to the Sponsor as soon as it is available or at least within one working day of the information becoming available.

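### Sections 9.1 and 9.3 use different causality standards and judges for an AR, a SAR and a related SAE, so an unexpected serious event judged only possibly drug-related can miss SUSAR reporting.

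*Combined protocol and SAP*

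**What the plan says.** The table in section 9.1 (Definitions) sets the test for an AR low: "a causal relationship between a trial medication and an AE is at least a reasonable possibility, i.e. the relationship cannot be ruled out". It also says who may apply it: "All cases judged by either the reporting medically qualified professional or the Sponsor as having a reasonable suspected causal relationship to the trial medication" count as adverse reactions.

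The SAR row does not refer back to the AR row. It starts again from an adverse event, requires that it be serious, and adds that it is, "in the opinion of the reporting Investigator, believed with reasonable probability to be due to one of the trial treatments".

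The SUSAR row then builds on the serious adverse reaction: "A serious adverse reaction, the nature and severity of which is not consistent with the information about the medicinal product in question".

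Section 9.2 refers back to 9.1 and adds no causality rule. Section 9.3 asks for an SAE to be reported to the REC and Sponsor when the Chief Investigator considers it both unexpected and related, where related means that "it resulted from administration of any of the research procedures". For each SUSAR, the causality recorded is the investigator's opinion. Section 9.4 has the PI assign causality, with the Chief Investigator, a delegate or an independent clinical reviewer stepping in where no local assessment can be obtained.

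**The concern.** A SAR would ordinarily be the serious subset of the ARs. Here it has a higher threshold (probability instead of possibility) and a narrower set of judges (the reporting Investigator, with the Sponsor not mentioned). The expedited reports in section 9.3 hang on the SUSAR label, which sits on top of the SAR. An event can therefore meet the plan's own definition of a reaction, be serious and be unexpected, yet not carry the label that triggers a prompt report.

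The gap matters in this population. Section 9.3 itself notes that complications are routine after extensive colorectal surgery, so serious events will often have competing explanations, and a link that cannot be excluded is a realistic grade. Section 2.1 names the higher cefuroxime dose as the risk above standard treatment. At stake are the individual safety reports for such events and the consistency of the SAR count that a larger trial would inherit from this pilot.

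**Working it through.** No arithmetic applies: the plan states no figure on this point. The check is to set the definitions side by side and run cases through them.

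| Label | Causality standard | Who judges | Source |
|---|---|---|---|
| AR | Possible; not ruled out | Reporting professional or Sponsor | 9.1 |
| SAR | Reasonably probable | Reporting Investigator | 9.1 |
| SUSAR | That of the SAR, plus unexpected | That of the SAR | 9.1; investigator's opinion again in 9.3 |
| Reportable SAE | Resulted from a research procedure, plus unexpected | Chief Investigator | 9.3 |

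Cases under the literal wording:

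1. *Serious, unexpected, link not ruled out but not thought reasonably probable.* AE, SAE and AR: yes. SAR: no, the threshold is not met. SUSAR: no, because it is not a SAR.
2. *Serious, unexpected, considered related by the Sponsor only.* AR: yes, under the either-party rule. SAR: no, because that row counts only the reporting Investigator's opinion. SUSAR: no.
3. *As case 1 or 2, but expected.* AR: yes. SAR: no. SUSAR: no under any causality standard, because the event is expected. The only loss is from the SAR count.
4. *Serious and believed reasonably probable by the reporting Investigator.* SAR: yes. SUSAR: yes if unexpected. No gap.

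What cases 1 and 2 can miss, all from section 9.3: the fax to the Sponsor within one working day, the REC report within 15 days, and expedited reporting to the MHRA.

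Does another route restore these reports? The SAE route in 9.3 does not depend on the SAR label and has a different judge, but its causality wording is no lower than the SAR test. Nothing in 9.2 to 9.4 restores the possibility standard or gives the Sponsor a causality role.

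What remains in place: under 9.3 the DMC receives a combined report of AEs, SAEs, ARs, SARs and SUSARs, and AE rates above expectation go to the REC and Sponsor. Under 9.4 the DMC reviews unblinded overall safety data. Cases 1 to 3 are visible there as SAEs and as ARs.

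**The case against.** The strongest reply is that the text is ambiguous and does not clearly exclude these events. The phrase serious adverse reaction in the SUSAR row can be read as an AR, defined two rows above, that is also serious. The word *suspected* in SUSAR points to the lower threshold too. On that reading cases 1 and 2 are SUSARs. Likewise, the Sponsor's exclusion from the SAR judgement rests on silence in that row; no sentence withdraws the either-party rule. This stands as a limit on how firmly the consequence can be put. It does not remove the problem, because two readings of one table lead to different reporting duties.

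A reader might infer that a possibly related serious event can never become a SAR or SUSAR, or can trigger no individual report. The documents do not support that. It needs the strictest reading, an event later judged reasonably probable becomes a SAR, and the Chief Investigator has a separate route for SAEs.

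A reader might also infer that the DMC would not see these events, or that well-known antibiotic complications would escape expedited reporting. Neither follows. The DMC gets them as SAEs and ARs. A SUSAR must also be unexpected, and 9.3 lists infections generally, as well as everything in the product characteristics, as expected. *C. difficile* infection, for example, falls among the expected infections whatever its causality grade.

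Finally, both arms receive cefuroxime under the same definitions, so no bias between arms is shown, and no stopping rule or endpoint uses the SAR count. That stands.

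**Conclusion.** The inconsistency is real and should be corrected. Sections 9.1 and 9.3 give three causality wordings with different judges, and nothing in 9.2 to 9.4 reconciles them. Taken as written, the plan's AR standard is not carried through to the categories that drive individual reporting.

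The exposure is limited to serious, unexpected events that are either possibly but not probably related, or considered related by the Sponsor alone. For those, the SUSAR reports can be missed. For expected events of the same kind, only the SAR tally is affected.

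No count can be attached to this. The documents give no SAE rate, no causality grading scale and no split between possible and probable, so any number would rest on assumption alone. The conclusion assumes that staff follow the literal wording of the SAR row; if they treat a SAR as a serious AR, the gap closes in practice but the text remains contradictory. Sample size, power and the primary analysis are unaffected.

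**What to change.** - In 9.1, define a SAR as an AR, including the rule that either the reporting professional or the Sponsor may judge it, that meets a seriousness criterion.
- In 9.1, define a SUSAR as a SAR that is unexpected.
- In 9.3, use the same reasonable-possibility standard for relatedness in the SAE route.
- Tabulate SARs for the DMC on that definition.

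This applies the plan's own AR standard consistently and needs only changes of wording. The price is a few more events to assess and report.
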